#### 7.10.2 Seizure Diary

Seizure diary data will be presented in a listing and summarized by overall treatment for the following assessments and for the data captured in the eCRF under Seizure Diary Review Form:

- Number of seizures
- Seizure type

[REDACTED]  
[REDACTED]  
[REDACTED]  
[REDACTED]  
[REDACTED]  
[REDACTED]  
[REDACTED]

#### 7.10.3 CGI-C

CGI-C assessment will be listed and summarized by visit using descriptive statistics for overall treatment.

### 7.11 Analysis of Pharmacokinetic Data

Concentrations data will be summarized in tables and figures when at least 3 subjects for overall treatment have non-missing data at the time point being summarized. Within individual subject concentration versus time profiles, whether graphical or tabular, all assayed concentrations will be presented, even when not summarized elsewhere.

Concentration summaries and corresponding figures/listing will be presented using PK Population. PK concentration data for blood and urine samples and volume of urine samples will be summarized for overall treatment by descriptive statistics of n, arithmetic mean, standard deviation (SD), coefficient of variation (CV), geometric mean, geometric CV, median, minimum, and maximum. Geometric CV is calculated as the square root of the exponentiated variance of the natural log transformed data minus 1 ( $SQRT(\exp(SD^2)-1)$ ) where appropriate.

## 7.12 Analysis of Safety Data

### 7.12.1 Adverse Events

All AEs will be coded to SOC and PT using Medical Dictionary for Regulatory Activities (Version 22.0 or later) and presented by subject in data listings.

A treatment-emergent adverse event (TEAE) is defined as any AE that began or worsened following the start of dosing of Treatment Period 1, Day 1 to Follow-Up.

A treatment-related AE is defined as any TEAE that is assessed by the Investigator as possibly, probably or definitely related to study drug.

Adverse event analyses will be conducted using the Safety Population.

The overall incidence of TEAEs (number and percentage of subjects) as well as the number of events will be summarized for mild TEAEs, moderate TEAEs, severe TEAEs, TEAEs assessed as at least possibly related, SAEs, TEAEs leading to study or drug discontinuation, SAEs related to study drug, life-threatening SAEs and SAEs resulting in death. All AE reports will also include the action taken as a result of the AE such as dose not changed, drug interrupted, drug withdrawn, dose increased, not applicable, or unknown.

The following TEAEs summaries will be presented (where applicable the number of patients (%)) and number of events will be summarized) by SOC and PT for overall treatment group:

- TEAEs
- Treatment-related TEAEs
- TEAEs leading to investigational product discontinuation
- Treatment-related TEAEs leading to investigational product discontinuation
- Serious TEAEs
- Treatment-related serious TEAEs
- TEAEs leading to death
- Treatment-related TEAEs leading to death.

All TEAEs will be summarized by SOC and PT using frequency counts and percentages (i.e., number and percentage of patients with an event); also the number of events will be presented

Tabulations will include an overall incidence of subjects reporting at least one AE, an overall incidence of TEAEs, and incidence within SOC and PT. Each patient may only contribute once (i.e., most severe occurrence) to each of the incidence rates, regardless of the number of occurrences.

For the incidence at the subject level by SOC, PT and relationship to study drug; if a subject experiences more than 1 event within the same SOC and PT, only the most related occurrence (in

descending order of definitely related, probably related, and possibly related) will be included in the incidence.

Listings of AEs, TEAEs, SAEs, TEAEs leading to death and TEAEs leading to study drug discontinuation will also be presented.

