Dosage, and Route of
Administration:**

Investigational product is a white to off-white powder. The dosage form received at each clinical study site is a glass bottle containing a nominal quantity of 100 mg of the powder JBPOS0101 active pharmaceutical ingredient (API) for reconstitution into an oral solution.

Sample Size:

Approximately, 50 patients will be screened of which around 35 patients will be enrolled to provide at least 26 completers. At least 7 of the patients enrolled must be between 6 months through 12 months of age at the time of informed consent.

Statistical Methods:

The primary endpoint is the incidence of treatment-emergent adverse events (TEAEs). Safety results will be reported using summary tables, listings, and figures, as appropriate, for all patients in the safety population.

The Medical Dictionary for Regulatory Activities (latest version) will be used to classify all AEs with respect to system organ class and preferred term. Adverse event summaries will include only TEAEs.

Prior and concomitant medications will be summarized according to the World Health Organization Drug Dictionary. Numerical laboratory test results, vital sign measurements, and ECG data will be summarized for observed values and change from screening/baseline. Shifts from screening/baseline will also be presented for clinical laboratory findings according to normal range criteria, physical and neurological examination findings, and overall ECG interpretation findings.

Data listings will be provided for protocol-specified safety data. The secondary endpoints include plasma PK parameters AUC, C_{min} , and C_{max} . Other PK parameters may be calculated, as appropriate. Plasma PK parameters will be presented in a summary table, as data allow. Relationship between plasma investigational product levels and response will be studied. The efficacy analysis serves as the explorative endpoint.

Version and Date of Protocol:

Version 2.0 and 15 September 2020

List of Abbreviations

Abbreviation	Definition
ACTH	adrenocorticotropic hormone
AE	adverse event
AMPA	α -amino-3-hydroxy-5-methyl-4-isoxazolepropionic acid
API	active pharmaceutical ingredient
AUC	area under the concentration-time curve
AUC ₀₋₂₄	area under the concentration-time curve during 24 hours
BASED	Burden of Amplitudes and Epileptiform Discharges
BID	twice daily
BMI	body mass index
BUN	blood urea nitrogen
CFR	Code of Federal Regulations
CGI-C	Clinical Global Impression of Change

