6.1.5 Adverse Events

6.1.5.1 Definitions of Adverse Events

The investigator is responsible for reporting all TEAEs that are observed or reported during the study, regardless of their relationship to the investigational product or their clinical significance.

An AE is defined as any untoward medical occurrence in a patient enrolled into this study regardless of its causal relationship to the investigational product. The patient's legal representative (parent[s]/caregiver[s]) will be instructed to contact the investigator at any time if any symptoms develop.

A TEAE is defined as any event not present before exposure to the investigational product or any event already present that worsens in either intensity or frequency after exposure to the investigational product.

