6.1.5.3 Eliciting and Documenting Adverse Events

Adverse events will be assessed from the time the patient's legal representative (parent[s]/caregiver[s]) signs the ICF until and including the Follow-Up visit, 14 days after the last dose of the investigational product.

Serious AEs that occur more than 14 days after the last dose of the investigational product need not be reported unless the investigator considers them related to the investigational product.

At every study visit, the patient's legal representative (parent[s]/caregiver[s]) will be asked a standard nonleading question to elicit any medically-related changes in the patient's well-being. They will also be asked if the patient has been hospitalized, had any accidents, taken any new medications, or changed concomitant medication regimens (both prescription and OTC medications).

In addition to patient observations, AEs identified from any study data (e.g., laboratory values, physical examination findings, and ECG changes) or identified from review of other documents (e.g., seizure diaries) that are relevant to patient safety will be documented on the AE page in the eCRF.

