### **3.8 Evaluation of Treatment Safety**

#### **3.8.1 Adverse Events**

An AE is defined as any untoward medical occurrence in a patient enrolled into this study regardless of its causal relationship to the investigational product. The patient's legal representative (parent[s]/caregiver[s]) will be instructed to contact the investigator at any time if any symptoms develop.

A TEAE is defined as any event not present before exposure to the investigational product or any event already present that worsens in either intensity or frequency after exposure to the investigational product.

All AEs will be reported or observed during the study will be recorded on the AE form in the eCRF. The AE and SAE reporting period begins after administration of study drug through the follow up visit. The Investigator will follow-up on all AEs observed or reported by the subject up to the end of the reporting period unless the event stabilizes and follow-up is no longer necessary. The Investigator will follow-up on SAEs until they are considered resolved or the outcome is known.

The following details will be collected for AEs: description of the AE, onset date/time, action taken with study drug (dose not changed, drug interrupted, drug withdrawn, dose increased, not applicable, or unknown), date/time of resolution, any additional treatment given, outcome

(recovered/resolved, not recovered/not resolved, recovered/resolved with sequelae, recovering/resolving, fatal or unknown), severity (mild, moderate, severe), seriousness (yes, no), relationship to study drug (unrelated, possibly, probably, definitely related or unknown), and whether the AE causes early termination of the subject.

The severity of AEs will be categorized as follows:

- Mild: These events require minimal or no treatment and do not interfere with the patient's daily activities.
- Moderate: An AE that is sufficiently discomforting to interfere with normal activities.
- Severe: These events interrupt a patient's usual daily activity and may require systemic drug therapy or other treatment. Severe events are usually incapacitating.

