## **Section 16.2.7**

### **Adverse Event Listings**

- Listing 16.2.7.1 All Adverse Events (Safety Population)
- Listing 16.2.7.2 Serious Treatment-Emergent Adverse Events by Subject (Safety Population)
- Listing 16.2.7.3 Treatment-Emergent Adverse Events Leading to Discontinuation of Study Drug by Subject (Safety Population)
- Listing 16.2.7.4 Treatment-Emergent Adverse Events Leading to Death by Subject (Safety Population)

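### The SAP defines a treatment-emergent event in two ways, and the definition in the analysis section drops late serious events that the protocol collects because they are judged drug-related

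*SAP*

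**What the plan says.** **Protocol.** Section 6.1.5.1 gives this TEAE definition: "any event not present before exposure to the investigational product or any event already present that worsens in either intensity or frequency after exposure". It sets no closing date. Section 6.1.5.3 assesses adverse events "until and including the Follow-Up visit, 14 days after the last dose of the investigational product". It adds that SAEs occurring later than that 14-day mark "need not be reported unless the investigator considers them related to the investigational product". The synopsis (Statistical Methods) names TEAE incidence as the primary endpoint and states: "Adverse event summaries will include only TEAEs".

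**SAP.** Section 3.8.1 repeats the protocol definition, including "any event already present that worsens in either intensity or frequency after exposure to the investigational product". The same section ends the AE and SAE reporting period at the follow-up visit and does not mention the protocol's exception for late related SAEs. Section 7.12.1 gives a second definition: "any AE that began or worsened following the start of dosing of Treatment Period 1, Day 1 to Follow-Up". It continues: "A treatment-related AE is defined as any TEAE that is assessed by the Investigator as possibly, probably or definitely related to study drug". Section 4 declares no change from the protocol.

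**The concern.** The two SAP definitions give different answers for the late serious events that the protocol keeps reportable. Under 3.8.1 such an event is a TEAE; under 7.12.1 it is not. Because 7.12.1 builds treatment-related on top of TEAE, an SAE that was reported only because it was judged related would be classed as not treatment-related in the analysis.

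A reader of the tables by SOC and PT could therefore see no related serious event when one had been reported. The result would depend on which definition was programmed, for the primary endpoint of a first study in infants and young children with this condition. Protocol section 7 asks for a protocol amendment when the primary endpoint definition or its analysis is changed in a major way, and the SAP does not acknowledge any change.

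**Working it through.** This is mainly a comparison of texts. The arithmetic covers the dates and the size of the effect on one table row.

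**1. Dates.** Protocol 3.1 stops the product on Day 42 and places Visit 7 on Day 56 ± 5 days.
- Nominal gap: 56 − 42 = 14 days, which reproduces the protocol's own figure.
- With the visit window: 51 − 42 = 9 days to 61 − 42 = 19 days. If the last dose falls on Day 41, the range is 10 to 20 days.

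**2. What Follow-Up means.** SAP 7.12.1 does not say whether it is the visit or the period, which protocol 3.1 gives as Days 43 to 56.
- If it is the visit, the TEAE window closes between Day 51 and Day 61. An SAE on Day 53 after a Day 51 visit would be outside it, although only 53 − 42 = 11 days after the last dose.
- If it is the period, the Day 53 event is inside. Events starting on Days 57 to 61 before a late Visit 7 would then be outside, although 6.1.5.3 collects them.

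**3. Path of one event.** Take an SAE with onset after Follow-Up on either reading, more than 14 days after the last dose and judged related.
- Protocol 6.1.5.3: reportable.
- SAP 3.8.1 reporting period: already closed.
- SAP 3.8.1 TEAE definition: counted.
- SAP 7.12.1 TEAE definition: not counted, and so not treatment-related.
- Tables 14.3.1.2 and 14.3.1.3 (all and related TEAEs), 14.3.1.6 and 14.3.1.7 (serious), 14.3.1.8 and 14.3.1.9 (if fatal): absent under 7.12.1.
- Listings 16.2.7.2 (serious TEAEs) and 16.2.7.4 (TEAEs leading to death, if fatal): absent under 7.12.1.
- Table 14.3.1.1 (overall summary): unclear. Its title refers to TEAEs, but 7.12.1 names its SAE, related-SAE and SAE-death rows without that label.
- Table 14.3.2.1 (deaths and other serious events) and Listing 16.2.7.1 (all adverse events): present, since neither is limited to TEAEs.

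**4. Size in one row.** The denominator is 35, because protocol 4.2.3 closes enrollment once 35 patients have begun Treatment Period 1. Exact (Clopper-Pearson) 95% intervals:
- 0/35: upper limit 1 − 0.025^(1/35) = 10.0%, so 0% (0 to 10.0%).
- 1/35 = 2.9%: lower limit 1 − 0.975^(1/35) = 0.07%; upper limit 14.9%, where P(X ≤ 1) = 0.025. So 2.9% (0.1 to 14.9%).

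**5. How likely.** The documents give no rate of late related SAEs. For an assumed per-patient risk p, the chance of at least one among 35 is 1 − (1 − p)^35:

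| Assumed p | Chance of at least one |
|---|---|
| 0.5% | 16% |
| 1% | 30% |
| 2% | 51% |
| 5% | 83% |

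**The case against.** The strongest reply is that ending TEAEs at Follow-Up matches the protocol's own assessment period. Later reporting is selective, since only SAEs judged related need be sent in. Adding those events to TEAE incidence makes treatment emergence depend on causality. With about 35 patients, any such event would in any case be shown individually in Table 14.3.2.1. This has weight: a bounded window is a legitimate choice, and the individual display limits the harm. It does not explain two definitions in one SAP, an undefined end point, or a rule that classes a related event as not treatment-related.

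A reader might also infer more than the documents support:

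- **That the event disappears from every table or from the report.** The overall-summary SAE rows are ambiguous, and one table and one listing still carry it.
- **That every death after Follow-Up is dropped.** Section 7.12.1 tests when the event began or worsened. A late death from an event that began or worsened inside the window still counts.
- **That the window certainly moves with the visit date.** That holds only if Follow-Up means the visit.
- **That 9 of 35 patients are expected to have no end date.** The difference 35 − 26 = 9 uses a minimum target of completers, which is not a forecast of dropout. What stands is narrower: early discontinuers are directed to Visit 6 assessments (protocol 4.2.2), and the SAP gives no rule for a patient without a Visit 7.

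**Conclusion.** The inconsistency is real and worth correcting before database lock. The SAP contains an open-ended TEAE definition and a bounded one, does not say which prevails, and does not define the end of the bounded one. If 7.12.1 is applied, as its place in the analysis section suggests, an SAE that protocol 6.1.5.3 keeps reportable because it is related is omitted from the TEAE tables by SOC and PT and from two TEAE listings. SAP 3.8.1 separately omits the protocol's late-reporting exception, while section 4 says nothing has changed.

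The size is one table row moving between 0/35 and 1/35 for each affected patient. That figure is illustrative. It assumes 35 treated patients, that such an event occurs, and that the row would otherwise be empty. No formal test is affected, because none is planned.

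**What to change.** - Use one TEAE definition in SAP 3.8.1 and 7.12.1: onset, or worsening in intensity or frequency, from first dose to the later of Visit 7 or 14 days after the patient's actual last dose, plus any later SAE reported because it is judged related. The last-dose anchor also supplies an end date for patients without a Visit 7.
- Include these late events in Tables 14.3.1.1 to 14.3.1.3 and 14.3.1.6 to 14.3.1.9 and in Listings 16.2.7.2 and 16.2.7.4, with a footnote giving days since last dose. The footnote lets a reader separate them from events found under scheduled assessment.
- Restore the protocol 6.1.5.3 exception in the reporting period of SAP 3.8.1.
- If the sponsor prefers the narrower window, define its end, declare it in SAP section 4 as a change from the protocol, and consider whether protocol section 7 then calls for an amendment.

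**Cost:** SAP wording and one programming flag, with no new data collection. Serious-event counts may look slightly less favourable.

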#### 7.12.2 Clinical Laboratory Assessments

Observed values and change from baseline for each parameter of continuous clinical laboratory values (hematology, coagulation, serum chemistry and urinalysis) will be summarized by overall and visit using descriptive statistics.

Shift from screening/baseline to post-baseline laboratory findings in normal range criteria will also be summarized.

A listing of all clinical laboratory data for each subject at each visit will be presented. Clinical laboratory values that are outside the normal ranges will be presented in a separate listing. The normal ranges will also be listed.

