4.1.1 Inclusion Criteria

Each patient must meet all the following criteria to be enrolled in this study:

1. Parent(s)/caregiver(s) fully comprehend and sign the ICF in accordance with applicable laws, regulations, and local requirements, understand all study procedures, and can communicate satisfactorily with the investigator and study coordinator.
2. Is a male or female from 6 months through 36 months of age at the time of informed consent.
3. Has clinical diagnosis of IS, confirmed by video-EEG analysis, and hypsarrhythmia on EEG at screening according to the Burden of Amplitudes and Epileptiform Discharges (BASED) scale score.
4. As assessed by the investigator, has no or partial response to at least 2 out of the 3 therapies of ACTH, vigabatrin, and glucocorticoids (i.e. prednisolone), or has no or partial response to at least 1 out of the 3 therapies of ACTH, vigabatrin, and glucocorticoids and is contraindicated to and/or refused by the patient's legal representative(s) for treatment with 1 or both other 2 therapies.

5. Has general good health (defined as the absence of any clinically relevant abnormalities as determined by the investigator) based on physical and neurological examinations, medical history, normal renal function, and ECG, and clinical laboratory values completed during the Screening Period visit (Visit 1).
6. Parent(s)/caregiver(s) is willing and able to comply with the study procedures and visit schedules in the opinion of the investigator.

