4.1.2 Exclusion Criteria

Patient meeting any of the following criteria will be excluded from the study:

1. Is considered by the investigator, for any reason (including, but not limited to, the risks described as precautions and warnings in the current version of the investigator's brochure for the investigational product) to be an unsuitable candidate to receive the investigational product.
2. Has known or suspected allergy to the investigational product.
3. Has known or suspected allergy to apple juice.
4. Has clinically significant renal impairment, defined as creatinine >1.5 mg/dL or blood urea nitrogen (BUN) $>2 \times$ upper limit of normal (ULN).
5. Has clinically significant liver dysfunction, defined as total bilirubin $\geq 2 \times$ ULN, or aspartate aminotransferase or alanine aminotransferase $\geq 3 \times$ ULN.
6. Has clinically significant abnormal laboratory values; the investigator may deem the patient eligible if he/she judges the laboratory values to be not clinically significant.
7. Has an ongoing or known history of human immunodeficiency virus infection, or chronic hepatitis B or C.
8. Has a clinically significant abnormality on ECG that, in the opinion of the investigator, increases the safety risks of participating in the study.
9. Has a neurodegenerative disorder as the underlying cause of IS.
10. Has a known history of aspiration pneumonia within the past year.
11. Has previously participated in another clinical study of the investigational product or received any investigational drug or device or investigational therapy within 30 days of study entry.

12. Has received therapy with felbamate, cannabinoids, ketogenic diet or vagus nerve stimulation within 14 days of screening.
13. Has received therapy with a medication known to be a CYP3A4 substrate and whose PK has been shown to be impacted in the presence of a CYP3A4 inhibitor within 14 days of screening (see [Appendix 13.3](#) for a non-exhaustive list of CYP3A4 substrates).
14. Has not remained at stable doses of all drugs used for treating epileptic seizures for at least 14 days prior to screening (except for rescue medications used for acute treatment of breakthrough seizures which are not known to be CYP3A4 substrates and whose PK has not been shown to be impacted in the presence of a CYP3A4 inhibitor [see [Appendix 13.3](#) for a non-exhaustive list of CYP3A4 substrates]).

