Liver enzymes/LFTs will be assessed in accordance with the guidelines presented in the US Food and Drug Administration (FDA) Guidance for Industry—Drug-Induced Liver Injury: Premarketing Clinical Evaluation (July 2009).

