Liver enzymes/LFTs will be assessed in accordance with the guidelines presented in the US Food and Drug Administration (FDA) Guidance for Industry—Drug-Induced Liver Injury: Premarketing Clinical Evaluation (July 2009).

Urine drug screen assessment will be performed locally at screening time point.

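### The SAP pre-specifies no threshold-based or joint ALT/AST–bilirubin summary to carry out the liver assessment promised in Protocol 6.1.4 and SAP 3.8.2

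*SAP*

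**What the plan says.** **The commitment.** Protocol 6.1.4 states: "Liver enzymes/LFTs will be assessed in accordance with the guidelines presented in the US Food and Drug Administration (FDA) Guidance for Industry", and identifies the document as the July 2009 guidance on drug-induced liver injury. SAP 3.8.2 repeats the sentence. Neither place names a threshold or an output. Laboratory results are among the primary safety endpoints (Protocol 7.1, SAP 2.4.1).

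**The analysis.** SAP 7.12.2 plans:
- observed values and changes from baseline by visit. Under SAP 7.1 this means n, mean, SD, median, minimum, maximum and quartiles;
- a categorical shift: "Shift from screening/baseline to post-baseline laboratory findings in normal range criteria will also be summarized";
- a by-subject listing of all laboratory data, a separate listing of out-of-range values, and the normal ranges.

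SAP Section 8 matches this with Tables 14.3.4.1 (abnormal results listing), 14.3.4.2 (observed and change) and 14.3.4.3 (shift), and Listings 16.2.8.1 and 16.2.8.2. SAP 7.1 keeps unscheduled and repeat assessments out of the safety summaries and shows them in listings only.

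**Who can enter.** Exclusion 5 (Protocol 4.1.2) removes a child at total bilirubin of 2 x ULN or more, or AST or ALT of 3 x ULN or more. For other abnormal laboratory values, exclusion 6 adds that "the investigator may deem the patient eligible if he/she judges the laboratory values to be not clinically significant". Inclusion 5 (Protocol 4.1.1) asks for no clinically relevant abnormality, again as the investigator judges.

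**The concern.** Drug-related liver injury shows in individual children: how far a test rises, from what starting level, and whether aminotransferases and bilirubin are raised in the same child. The planned summaries treat each test separately, at each scheduled visit, and grade it only against the normal range. The stated liver assessment therefore has no summary with a threshold, a count or a denominator behind it.

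The SAP handles another safety domain differently. SAP 7.12.4 lists and summarizes ECG results that meet pre-specified limits, which it tabulates by age. Liver tests have no equivalent.

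At stake is whether the study report can say how many of about 35 treated children had a marked or joint liver abnormality, or whether the reader must work that out from listings.

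**Working it through.** The documents give no liver event rate or precision figure to reproduce. The check is therefore whether the planned outputs can display the signal. The ALT courses and event rates below are illustrative assumptions. The shift categories are taken as low, normal and high, with high meaning above 1 x ULN.

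**1. Shift table.** Baseline values are chosen below the exclusion 5 limit of 3 x ULN.

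| Baseline (x ULN) | Post-baseline (x ULN) | Ratio to baseline | Shift cell |
|---|---|---|---|
| 0.8 | 1.2 | 1.2/0.8 = 1.5 | Normal to High |
| 0.8 | 10 | 10/0.8 = 12.5 | Normal to High |
| 1.5 | 8 | 8/1.5 = 5.3 | High to High |
| 2.9 | 10 | 10/2.9 = 3.4 | High to High |

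The first two rows cannot be told apart, and this holds even if no child enters with raised enzymes. The last two register as no shift.

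**2. Descriptive statistics.** Take one child rising from 2.9 to 10 x ULN, with all others unchanged. The change is 10 − 2.9 = 7.1 x ULN.
- Effect on the mean change: 7.1/35 = 0.20 x ULN with 35 children, and 7.1/26 = 0.27 x ULN with 26.
- With 35 children, the median, Q1 and Q3 of change all stay at 0.
- The maximum change is 7.1 x ULN, so the rise is visible there if it falls at a scheduled visit.

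**3. Joint signal.** Suppose two children both start at 0.8 x ULN on ALT and bilirubin. In case A, at one visit, the first child reaches ALT 10 x ULN and bilirubin 2 x ULN, and the second is unchanged. In case B the first child has the ALT rise and the second has the bilirubin rise. The set of ALT values is the same in A and B, and so is the set of bilirubin values. Every planned by-analyte statistic and shift count is therefore identical. Only patient-level output separates A from B.

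**4. Timing.** Scheduled laboratory days are Screening, 7, 28 and 42 (SAP 3.8.2). The 15 mg/kg step starts on Day 15 and tapering on Day 29 (Protocol 3.1), so Day 28 is the only nominal laboratory day on the top dose. Protocol 6.1.4 calls for further assessments after a clinically significant value. Where these are unscheduled or repeat tests, SAP 7.1 keeps them out of the summaries, so a peak found that way would appear only in listings.

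**5. How few cases to expect.** P(at least one case) = 1 − (1 − p)^n.

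| Assumed true rate p | n = 35 | n = 26 |
|---|---|---|
| 1% | 0.30 | 0.23 |
| 3% | 0.66 | 0.55 |
| 5% | 0.83 | 0.74 |
| 10% | 0.98 | 0.94 |

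Any signal is likely to rest on very few children, which is where averages help least. If a defined count were zero, the exact one-sided 95% upper bound, 1 − 0.05^(1/n), would be 8.2% for n = 35 and 10.9% for n = 26. Without a defined count, no such statement can be made.

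**The case against.** A reader might infer that the SAP offers only mean changes and low/normal/high shifts, or that a liver signal could not be seen in any planned summary. The documents do not support either reading.
- Maxima are planned. A large rise in one test at a scheduled visit would show in the maximum observed value and the maximum change.
- All results and the normal ranges are listed by child. ULN multiples can be worked out and ALT/AST matched to bilirubin by hand. With three scheduled post-baseline draws in about 35 children there are roughly 3 x 35 = 105 sets, so manual review is feasible.
- Clinically significant changes from screening go on the adverse event page (Protocol 6.1.4, SAP 3.8.2). Worsening of an existing condition counts as treatment-emergent (Protocol 6.1.5.1), so a child already high at entry is not invisible.
- The DSMB reviews safety data after 5, 10, 20 and 30 children complete Treatment Period 1 (Protocol 6.4).

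Two further points are fair. Inclusion 5 and exclusion 6 narrow the group entering with raised enzymes, and the documents do not show how many such children would enrol. The guidance itself is not reproduced, so the documents cannot show that it requires any particular table.

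All of this stands, and it limits the point. It does not supply the missing summary. The maximum observed value is not tied to that child's baseline. The maximum change does not show the starting level. Neither is tied to the other liver tests. Listings carry no case definition or count. Adverse event reporting of laboratory changes depends on the investigator's judgement of clinical significance.

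**Conclusion.** The point holds as a gap in pre-specification. The liver commitment in Protocol 6.1.4 and SAP 3.8.2 has no threshold-based or joint summary in SAP 7.12.2 or Section 8. The normal-range shift cannot grade a new elevation or register worsening from high. Unscheduled and repeat tests do not reach the summaries. A joint case would be found only by manual review of listings or through investigator-judged adverse event reporting.

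It does not follow that a true signal would be missed or reported as absent, since several planned routes could reveal it among about 35 children. Nor does the point rest on what the FDA guidance contains. The comparison is between the documents' own commitment and their own output list.

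The size shown (no shift and a 0.20 x ULN change in the mean for a child reaching 10 x ULN) depends on illustrative courses and on the other children being unchanged. The grading failure and the loss of the joint signal do not depend on those particular values. This is a worthwhile, inexpensive improvement to a primary safety analysis.

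**What to change.** Add one table to SAP 7.12.2 and to the output list in SAP Section 8:
- for each treated child, the peak post-baseline ALT, AST and total bilirubin as a multiple of ULN, set against that child's baseline multiple;
- derived from all post-baseline results, including unscheduled and repeat tests, as a stated exception to the general rule in SAP 7.1;
- the number and percentage of children with ALT or AST at 3 x ULN or more, with bilirubin at 2 x ULN or more, and with both;
- a short listing of those children by study day and dose level.

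The cut-offs are those already in exclusion 5. They serve here only as reporting categories and not as a clinical rule. Keep the planned descriptive statistics, shift table and listings.

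The data are already collected, so the cost is slightly more programming.
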